3.7.2.1 Local Cutaneous Reactions at the Injection Site

Local cutaneous reaction at injection site (LCRIS) is defined as (A) moderate or severe Injection Site Erythema, Swelling, Pruritus, Pain or Tenderness that started on the day of injection, persisted for at least two days, i.e. event onset date on the day of injection and resolution date not on the day of injection or the day after the injection, will be included. Events with onset date on the day of injection and missing resolution date will also be included; or (B) any AE at the injection site, regardless of severity, that leads to discontinuation of study drug, where AE at the injection site is the principal reason for discontinuation.

Percentage of injections leading to local cutaneous reaction at the injection site will be calculated as follows for each subject: $(A/B)*100$, where A=number of injections with a LCRIS, and B=total number of injections. Doses that are split across multiple injections are counted as a single injection.

3.7.2.2 Flu-like Reactions

Flu-like reactions will also be summarized by preferred term.

Flu-like reactions are defined as either (A) flu-like illness or (B) Pyrexia or feeling hot or body temperature increased, plus at least two of the following: Chills, Myalgia, and Arthralgia, starting on day of injection or the next day.

Percentage of injections leading to flu-like reactions will be summarized using the descriptive statistics.

Percentage of the injections leading to flu-like reactions will be calculated as follows for each subject: $(A/B)*100$, where A=number of injections leading to flu-like reactions, and B=total number of injections.

Flu-like reactions will be listed by preferred term.

3.7.2.3 AE of special interest (AESI): Platelet reduction

Per protocol, severe reductions in platelet count $< 50,000/\text{mm}^3$ accompanied by a major bleeding (MB) event or clinically-relevant non-major bleeding (CRNMB) event, or platelet count of $< 25,000/\text{mm}^3$ independent of a MB or CRNMB event are considered as AESI. The AEs meeting the AESI criteria will be captured in the AE CRF page with a check box to indicate. AESI will be summarized by preferred term.

3.7.3 Laboratory Measurements

Chemistry, hematology, coagulation, complement and urinalysis (result, change and percent change from baseline) will be summarized by treatment group and each post-baseline visit. All ALT, AST, and Platelet data from both the central and local laboratories will be summarized. For the rest of the parameters, only the central laboratory values will be summarized. For urinalysis, only P/C ratio, Protein, and Urine Creatinine will be summarized.

For ALT and AST, the number and percent of subjects falling in each of the following categories will be tabulated by treatment group:

- ALT/AST > 3 x ULN, confirmed
- ALT/AST > 5 x ULN, confirmed

A confirmed value is based on a consecutive lab value performed on a different day to, but within 7 days of, the initial value. If that value is in the same or worse category then the initial value is confirmed. If the consecutive value is in a better category then the initial value is confirmed using the consecutive value category. If there is no retest within 7 days then the initial value is presumed confirmed.

If there are multiple results on the same day (no matter from the same lab vendor or different lab vendors), then the worst value will be utilized in the analysis.

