6.2. Laboratory Assessments

Laboratory analyte samples will be collected throughout the study. A list of these analytes is contained in [Appendix B](#). Blood chemistry should be taken after fasting for at least 8 hours. During this time the patient can drink water and they should ensure that they consume sufficient water in order to not become dehydrated.

If the platelet value, serum creatinine or liver enzyme tests are uninterpretable (e.g., due to clumping, hemolysis or quantity not sufficient) or missing a repeat blood specimen should be re-drawn as soon as possible (ideally within 7 days). Due to time constraints, a local lab draw is recommended if a repeat blood specimen is necessary to continue dosing at any time after Study Day 1 to Study Day 8. If there is suspicion of EDTA mediated platelet clumping, a repeat platelet count should be collected in a sodium citrate tube as soon as possible.

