10.6.2. Safety Analysis

The safety analysis will be conducted on the Safety Set.

Treatment duration and amount of Study Drug received will be summarized by treatment group. Subject incidence rates of all treatment-emergent AEs will be tabulated by Medical Dictionary for Regulatory Activities (MedDRA) coding system by system organ class, preferred term, relationship to Study Drug, and severity. Narratives of treatment-emergent deaths, serious and significant AEs, including early withdrawals due to AEs, will also be provided.

All treatment-emergent AEs, all treatment-emergent AEs potentially related to Study Drug, all treatment-emergent serious AEs, all treatment-emergent serious AEs potentially related to Study Drug, and treatment-emergent Adverse Event of Special Interest (AESI) will be summarized.

Laboratory tests to ensure subject safety including chemistry panel, complete blood count with differential, coagulation panel, etc., will be summarized by study visits for each treatment group. These safety variables will also be presented as change and percent change from Baseline over time after Study Drug administration, as appropriate.

Vital sign and ECG measures will be tabulated by treatment group. In addition, the number of subjects who experience abnormalities in clinical laboratory evaluations will be summarized by treatment group.

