3 ANALYSIS PLAN

3.1 General Overview of Analyses

Descriptive summary statistics including number of subjects, mean, median, standard deviation, standard error of mean, 25th percentile, 75th percentile, minimum, and maximum for continuous variables, and counts and percentages for categorical variables will be used to summarize most data. All statistical tests will be conducted using 2-sided tests with 5% Type I error rate unless otherwise stated.

[figure not shown]
PK parameters will be summarized using include number of subjects, mean, standard deviation, coefficient of variation (CV), geometric mean, median, minimum, and maximum.

Baseline definition:

The baseline for plasma AGT will be define as the average of all values on or after Study Day -7 and prior to the first dose of Study Drug. The baseline for all other assessments will be defined as the last non-missing measurement prior to the first dose, unless otherwise specified.

Analytical visits:

Data will be summarized using the visit labels provided in the data. Multiple results with the same visit label will be averaged. Results with visit labels as "Unscheduled" will not be included in the by-visit summary tables and figures except for determining baseline and the analysis of confirmed ALT/AST category (see section 3.7.3) but will be presented in data listings.

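### The SAP does not carry out, for potassium and renal tests, the by-arm count of subjects with laboratory abnormalities that protocol 10.6.2 promises

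*Combined protocol and SAP*

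**What the plan says.** Protocol 10.6.2 (Safety Analysis) states that "the number of subjects who experience abnormalities in clinical laboratory evaluations will be summarized by treatment group". It defines no thresholds for this count.

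SAP 3.7.3 (Laboratory Measurements) summarises results, change and percent change by arm and visit. Its one categorical laboratory analysis is for liver enzymes: "For ALT and AST, the number and percent of subjects falling in each of the following categories will be tabulated by treatment group", the categories being confirmed values above 3 and above 5 times ULN. Central and local values are both used for ALT, AST and platelets. After that, "For the rest of the parameters, only the central laboratory values will be summarized".

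SAP 3.1 (Analytical visits) says that results labelled as unscheduled "will not be included in the by-visit summary tables and figures except for determining baseline and the analysis of confirmed ALT/AST category", "but will be presented in data listings". It also says: "Multiple results with the same visit label will be averaged".

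SAP 3.7.2.3 summarises platelet events of special interest: counts below 25,000/mm³, or below 50,000/mm³ with major or clinically relevant non-major bleeding.

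On retesting, protocol 8.5 asks for confirmation on a new specimen, ideally within 3 days and ideally in the same laboratory. Separately, for samples that are missing or cannot be interpreted, protocol 6.2 says that "a local lab draw is recommended if a repeat blood specimen is necessary to continue dosing" early in dosing. That instruction covers platelets, serum creatinine and liver enzymes.

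**The concern.** Protocol 2.2 names hyperkalemia, hypotension and acute renal failure as the complications of combining RAAS agents, and suggests that this drug's renal-sparing action may improve on that record. Safety against placebo is a stated objective (1.1.3). How many subjects in each arm reached the trial's own potassium and renal action levels is therefore among the most informative safety comparisons the study can offer.

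The SAP recognised that confirming a threshold needs unscheduled samples, and made an exception for them, but only for ALT/AST. Potassium and the renal tests get neither a threshold count nor the unscheduled and local results that would feed one. The protocol's commitment is left undefined for the tests where it matters most.

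**Working it through.** The documents give no figure to reproduce here. The check sets sections side by side, followed by two small illustrations. SAP statements refer to the visible text.

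**1. Protocol rules against SAP counts**

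| Protocol rule | Section | Counted by arm in the SAP? |
|---|---|---|
| Potassium ≥ 5.5 mmol/L, confirmed (hold) | 8.5.2 | No |
| Potassium ≥ 6.0, or ≥ 5.5 with new ECG changes (stop) | 8.6.4 | No |
| Creatinine up ≥ 0.3 mg/dL and ≥ 40%, confirmed (stop) | 8.6.2 | No |
| eGFR down 30%, confirmed (stop) | 8.6.2 | No |
| UPCR ≥ 500 mg/g, confirmed (stop) | 8.6.2 | No |
| Platelets 50,000 to < 75,000/mm³ (pause) | 8.6.3 | No |
| Platelets 25,000 to < 50,000/mm³ (discontinue) | 8.6.3 | Only with qualifying bleeding (special-interest event) |
| Platelets < 25,000/mm³ (discontinue) | 8.6.3 | Yes (special-interest event) |
| ALT/AST > 3x and > 5x ULN, confirmed | 8.5.1, 8.6.1 | Enzyme level yes; added conditions (duration, bilirubin, INR, symptoms) no |
| ALT/AST > 8x ULN, confirmed (stop) | 8.6.1 | Not as its own category |

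**2. Which results reach a summary**

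Appendix A has weekly visits from Day 8 to Day 50, then gaps of 64 − 50 = 14, 78 − 64 = 14, 106 − 78 = 28 and 127 − 106 = 21 days. A retest within 3 days of a Day 15 sample falls on Days 16 to 18. The next visit is Day 22, and its ±2-day window opens on Day 20. The retest is then an extra sample, and one of two things happens:

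- If labelled as unscheduled, it is listed but left out of the by-visit tables.
- If given the visit's label, it is averaged with the first value. For example, 5.9 and 5.0 mmol/L average to (5.9 + 5.0)/2 = 5.45, below 5.5. This removes an initial crossing from view. It would not hide a confirmed one, since two values of at least 5.5 average to at least 5.5.

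A locally measured creatinine repeat, which protocol 6.2 encourages early in dosing for unusable samples, is excluded by the central-only rule in any case.

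**3. Size**

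About 30 subjects randomised 2:1 gives 30 × 2/3 = 20 active and 10 placebo.

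- One active subject crossing: incidence 1/20 = 5%. If that subject's potassium rises by 1.5 mmol/L (assumed), the arm mean moves by 1.5/20 = 0.075 mmol/L.
- Chance of at least one crossing in an arm of n subjects at true rate p: 1 − (1 − p)^n. The rates are assumed.

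| Assumed p | Active, n = 20 | Placebo, n = 10 |
|---|---|---|
| 2% | 33% | 18% |
| 5% | 64% | 40% |
| 10% | 88% | 65% |
| 15% | 96% | 80% |

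Even at modest rates, one or more crossings is a realistic outcome, so the missing table would probably not be an empty one.

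**The case against.** The strongest reply is that the information is not lost. Four parts of it are right.

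- Protocol 9.3.1 makes a laboratory deterioration an adverse event if it changes study treatment, and treatment-emergent events are tabulated by arm (SAP 3.7.2). A reader might infer that a subject stopped for hyperkalemia could be missing from every comparative table. The documents do not support that.
- Unscheduled results are listed, and protocol 10.6.2 adds narratives for serious and significant events. They are kept out of by-visit summaries, not discarded.
- The descriptive statistics include the minimum and maximum (SAP 3.1). It would be wrong to say the safety assessment rests on visit means: a scheduled central extreme would show as a visit maximum. Chemistry is drawn at every visit from Day 1, so the initial crossing will often be a scheduled result.
- Protocol 6.2 deals with missing or unusable platelet, creatinine and liver samples. It might be read as sending potassium retests or threshold confirmations to local laboratories. It does not, and protocol 8.5 prefers the original laboratory.

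A further argument is that a per-subject count is not a by-visit table, so the rule on unscheduled results would not bind it. But the confirmed ALT/AST count is also per subject, and the SAP still wrote an exception for it. The central-only rule has no such limit either.

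The adverse event route also does not reproduce the thresholds:

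- Findings judged not clinically significant are not adverse events, and a diagnosis is preferred to a laboratory term (9.5.1).
- Use of the CTCAE-based grades is optional (9.4.3.2), and their cut-points differ. In Appendix D a potassium of exactly 5.5 mmol/L is mild and exactly 6.0 moderate, although these values meet the hold and stop levels.
- Creatinine rising from 0.7 to 1.0 mg/dL is up 0.3 mg/dL and 0.3/0.7 = 43%. If confirmed, this meets the stopping rule. With a normal baseline it receives no grade if ULN is 1.0 or higher (assumed; the documents give no ULN).
- Events leading to drug discontinuation are listed, not tabulated (SAP 3.7.2).

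One can also say that protocol 10.6.2 still stands and nothing revokes it. True, but without thresholds, data source or confirmation rule it cannot be programmed.

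**Conclusion.** The point holds as a reporting gap. For potassium and renal tests, the SAP does not implement the protocol's by-arm count of laboratory abnormalities. For platelets it covers only the special-interest criteria, and for liver enzymes it omits the 8x ULN stop. Crossings may be visible elsewhere, but no table counts them by protocol threshold, and the results that confirm a crossing will often be outside the summaries.

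The consequence is limited. The primary analysis, subject protection and dosing rules are untouched, and in a study of about 30 subjects a reader could reconstruct the counts from listings. What is lost is a prespecified comparison on hyperkalemia and renal function, which the protocol itself singles out. The change should be made as a cheap improvement to the safety analysis.

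This rests on the visible SAP text, on arms of about 20 and 10, and on confirmation samples being taken near the protocol's preferred 3 days. The 1.5 mmol/L rise and the crossing rates are illustrations, not estimates.

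**What to change.** Extend the ALT/AST table in SAP 3.7.3 to the number and percent of subjects in each arm who ever meet each threshold already written in protocol 8.5.2, 8.6.1 (including ALT/AST > 8x ULN), 8.6.2, 8.6.3 and 8.6.4. Specify that the table:

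- uses all post-dose results, whether central or local, scheduled or unscheduled, with the laboratory source flagged in the listing;
- shows initial and confirmed crossings separately, under a stated rule modelled on the ALT/AST one, covering the retest window and what happens when no retest exists;
- does not average repeats that share a visit label. SAP 3.7.3 has a worst-value-of-the-day rule next to the ALT/AST definition; say whether it applies to all tests;
- brings in ECG data for the potassium criterion that requires ECG changes, since laboratory values alone cannot establish it.

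Also widen the exception in SAP 3.1 from confirmed ALT/AST to this whole table. The by-visit summaries can stay as they are.

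The cost is one more safety table and its programming, from data already collected. No clinical threshold or dosing rule changes.

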8.6.3. Stopping Rule for Platelet Count Results

In the event of any platelet count less than 75,000/mm³, monitoring frequency and dosing should be adjusted as recommended in the table below.

Table 6: Actions in Patients with Low Platelet Count

Confirmed Platelet Count	Dosing	AESI?	Monitoring
$\geq 75,000/\text{mm}^3$	Yes	No	
 Monitor weekly
$< 75,000/\text{mm}^3$ to $50,000/\text{mm}^3$, in the absence of major bleeding or clinically-relevant non-major bleeding (defined below)	Pause	No	
 Monitor at least twice per week until 3 successive values above $75,000/\text{mm}^3$. Then monitor weekly until values normalize. The suitability of the patient for continued dosing will be determined by the Investigator in consultation with the Study Medical Monitor and will be based on factors such as the original rate of decline in the patient's platelet count, whether any bleeding events were experienced, and the speed of recovery of platelet count after interruption of dosing. The patient must have 3 successive values above $100,000/\text{mm}^3$ before continued dosing is considered. Perform additional labs in Table 5
$< 50,000/\text{mm}^3$ to $25,000/\text{mm}^3$	Permanently Discontinue	Yes, if only accompanied by a major bleeding event or CRNMB event, subject to 15-day expedited reporting	
 Monitor at least twice per week until 3 successive values above $75,000/\text{mm}^3$. Then monitor weekly until values normalize. A hematologist consultation may be considered at the discretion of the Investigator and Study Medical Monitor Perform additional labs in Table 5
$< 25,000/\text{mm}^3$	Permanently Discontinue	Yes, subject to 15-day expedited reporting	
 Monitor daily until 2 successive values above $25,000/\text{mm}^3$. Then monitor twice per week until 3 successive values above $75,000/\text{mm}^3$. Then monitor weekly until values normalize. Administration of steroids* and a hematologist consultation is recommended Perform additional labs in Table 5

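### The SAP plans no laboratory-derived count of subjects crossing platelet thresholds, and its visit-label rules can omit or blunt the counts that pause or stop dosing

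*Combined protocol and SAP*

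**What the plan says.** Protocol 10.6.2 commits to a summary in which "the number of subjects who experience abnormalities in clinical laboratory evaluations will be summarized by treatment group". It names no parameters or cut-offs.

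SAP 3.7.3 turns this into subject counts for two parameters: "For ALT and AST, the number and percent of subjects falling in each of the following categories will be tabulated by treatment group". The categories are confirmed values above 3 and above 5 times the upper limit of normal. For platelets, 3.7.3 plans result, change and percent change by visit, and adds: "All ALT, AST, and Platelet data from both the central and local laboratories will be summarized".

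SAP 3.1 governs what enters a by-visit table. Results labelled Unscheduled "will not be included in the by-visit summary tables and figures except for determining baseline and the analysis of confirmed ALT/AST category"; they do go into the listings. For repeated results, "Multiple results with the same visit label will be averaged".

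SAP 3.7.2.3 summarizes platelet adverse events of special interest (AESI) by preferred term. The source is the case report form: "The AEs meeting the AESI criteria will be captured in the AE CRF page with a check box to indicate".

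Protocol 8.6.3, Table 6, pauses dosing for counts below 75,000 down to 50,000/mm³ without major or clinically relevant non-major bleeding, and stops it permanently below 50,000/mm³.

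**The concern.** Platelet reduction is the only AESI in the study, and protocol 3.3 justifies the sample size by safety and tolerability. The natural question at the end is how many subjects in each arm fell below the pause level and how many below the stop level. No planned table answers it from the laboratory data.

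The SAP already accepts that a threshold table needs unscheduled retests, because it makes that exception for ALT and AST. SAP 3.7.3 also groups platelets with those two enzymes as the parameters summarized from local as well as central laboratories. Platelets are nevertheless left out of both the category table and the exception. The counts most likely to decide a pause or a stop may therefore be the ones that the tables drop or average.

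**Working it through.** The plan gives no figure to reproduce. The check sets the rules side by side and follows a few counts through them.

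**1. Treatment of the parameters in the SAP**

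| Feature | ALT/AST | Platelets |
|---|---|---|
| Central and local results used (3.7.3) | Yes | Yes |
| By-visit descriptive statistics (3.7.3) | Yes | Yes |
| Subjects counted by threshold (3.7.3) | Yes, two categories | None |
| Confirmation rule (3.7.3) | Yes, consecutive value on another day within 7 days | None |
| Unscheduled post-baseline values used in a table (3.1) | Yes, for the categories | No |

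**2. Where the deciding counts fall**

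Hematology is scheduled in Appendix A on Days 1, 3, 8, 15, 22, 29, 36, 43, 50, 64, 78, 106 and 127. The protocol asks for further counts:

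- a confirmatory retest, ideally within 3 days (8.5);
- a recheck of any unreportable count before dosing continues (8.5.4);
- a count after a minor bleed (8.5.5);
- after a count below 75,000, the Table 6 instruction that begins "Monitor at least twice per week until 3 successive values above" 75,000/mm³, with daily counts below 25,000;
- weekly counts for 4 weeks after treatment ends (8.5.4). From the last dose on Day 36 these fall on 36 + 7k = Days 43, 50, 57 and 64. Day 57 has no visit.

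From Day 8 to Day 50 there is one scheduled count a week, so twice-weekly monitoring puts at least 2 − 1 = 1 count a week outside the schedule.

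**3. What happens to an extra count**

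The documents do not say how extra counts are labelled, so both possibilities are followed. The platelet values are illustrations.

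*Labelled Unscheduled.* The Day 15 sample is unreportable, the repeats are 62,000 and 64,000, and dosing is paused. The repeats are kept out of the by-visit tables and missing values are not imputed (SAP 3.3.2), so the subject adds nothing to the Day 15 platelet summary. A table of lowest counts would show this subject below 75,000, for any count and for confirmed counts.

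*Given the visit label.* SAP 3.1 averages the results. For two counts x and y and a threshold T, the mean is at or above T when y ≥ 2T − x. With x = 62,000 and T = 75,000, y ≥ 150,000 − 62,000 = 88,000, so 62,000 followed by 88,000 is shown as 75,000, which is not below the threshold. Two counts that are both below T always average below T, so a confirmed pair alone is not lifted over it, only blunted: (62,000 + 64,000)/2 = 63,000. A third, recovering count under the same label can lift the pair: (62,000 + 64,000 + y)/3 ≥ 75,000 when y ≥ 225,000 − 126,000 = 99,000.

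**4. What the by-visit minimum adds**

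SAP 3.1 includes the minimum. A minimum below 75,000 shows that at least one subject in the arm was low at that visit. It does not show how many, or whether low minima at different visits belong to one subject.

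**5. Scale**

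About 30 subjects at 2:1 gives 30 × 2/3 = 20 active and 30 × 1/3 = 10 placebo. One subject is 1/20 = 5% or 1/10 = 10% of an arm.

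**The case against.** The strongest reply is that low counts remain traceable. Protocol 9.3.1 lists as an adverse event a laboratory deterioration that leads to a change in study treatment, and a platelet-driven pause or stop fits that description. SAP 3.7.2 tabulates treatment-emergent events by preferred term and severity, Appendix D grades platelet decreases at 75,000 and 50,000, and events leading to drug discontinuation are listed separately. Every count is in the listings, and the minimum shows the lowest value at each scheduled visit. One may add that 10.6.2 fixes no parameters, and that the promise to summarize all platelet data concerns the laboratory source rather than the visit label.

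Most of this stands, and it limits the point. A reader might infer that a paused subject could be in no table at all; 9.3.1 and SAP 3.7.2 do not support that. They do not replace a laboratory count, however. Appendix D grading is optional (9.4.3.2), 9.5.1 keeps abnormalities judged not clinically significant out of adverse event reporting, and a preferred-term row gives no platelet value.

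A reader might also infer that Table 6 and protocol 9.3.4 define the AESI differently, because the first column of Table 6 is headed "Confirmed Platelet Count" and 9.3.4 does not mention confirmation. The documents do not support this. Both require bleeding below 50,000 and drop that condition below 25,000, and SAP 3.7.2.3 repeats the rule. Comparing the two rules for counts from 1,000 to 200,000 in steps of 500, with and without bleeding, gave no difference wherever Table 6 has a row. The one combination without a row, 50,000 to below 75,000 with bleeding, is not an AESI under 9.3.4. That comparison tests thresholds and not confirmation, but the header belongs to a table of actions and agrees with the general retest rule in 8.5; it is not a second definition. Because AESI status comes from a check box, averaging under SAP 3.1 cannot alter it.

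**Conclusion.** The gap is real and minor. As written, the SAP gives no laboratory-derived count of subjects by platelet threshold, and its visit-label rules can omit or blunt the nadirs behind the Table 6 pause and stop rules. This falls short of the 10.6.2 commitment and of the treatment that the SAP gives ALT and AST.

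The effect is on the reporting of safety. No efficacy result, dosing rule or expedited-reporting rule changes, and no data are lost. The size cannot be estimated: the documents give no rate of low counts, and the effect depends on how sites label extra counts, either as Unscheduled (omitted) or under a visit label (averaged). A reader might take the share of monitoring counts that fall between visits as a measure of lost information. That is not supported, because the share depends on an assumed duration of intensive monitoring and on the labelling. What can be said is that one subject more or less is 5 percentage points among about 20 active subjects.

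**What to change.** Two changes, both in the SAP.

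- **SAP 3.7.3:** add a table, by treatment group, of the number and percent of subjects whose lowest post-Baseline platelet count is <100,000, <75,000, <50,000, <25,000 and <10,000/mm³. Show it for any count and for confirmed counts, with the ALT/AST confirmation rule. Use scheduled, unscheduled, central and local results. Exclude uninterpretable samples, such as clumped ones, and use the citrate repeat described in protocol 6.2 instead.
- **SAP 3.1:** add *and the platelet category analysis* to the exceptions for unscheduled results.

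The cost is one extra safety table from counts already collected. Visits, blood draws, case report forms, the protocol and Table 6 stay as they are.
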